**Title:** Diagnostic Accuracy of Artificial Intelligence, CBCT, and Clinical Examination in Detecting Number of Root Canals in Conventional and Retreated Maxillary and Mandibular Molars

NCT Number: "Pending"

Date: 29/10/2024

Introduction: Accurate root canal detection is crucial for successful endodontic treatment, particularly in complex molar cases. Conventional methods, such as clinical examination and cone-beam computed tomography (CBCT), have their limitations, as high radiation exposure. Recent advancements in Artificial Intelligence (AI) have shown promise in improving diagnostic accuracy. This study aims to compare the effectiveness of AI, CBCT, and clinical examination using a dental operating microscope (DOM) in detecting root canals in upper first, upper second, and lower first molars, in both conventional and retreatment cases.

Methods: CBCT scans from 210 patients requiring non-surgical root canal therapy or re-treatment were selected. The scans were analyzed using three detection methods: clinical examination via DOM, interpretation by two experienced endodontists using CBCT, and an AI convolutional neural network (CNN) software (Diagnocat). The detected number of root canals was recorded and compared across the three methods. Statistical analysis was performed to evaluate the diagnostic accuracy, including sensitivity, specificity, and agreement between methods.

Results: AI detected a significantly higher number of molars with three or four canals compared to clinical examination and CBCT in conventional treatment cases (P < 0.001). In retreatment cases, AI demonstrated a similar trend, with one case of five root canals detected clinically but missed by both CBCT and AI. Overall, AI showed higher diagnostic accuracy (88.2%) compared to clinical examination and CBCT. There was no significant difference in AI accuracy between molar types, though the upper first molar had the highest accuracy (93.9%).

Conclusion: AI demonstrated higher accuracy in detecting root canals compared to CBCT and clinical examination in both conventional and retreatment cases, particularly in upper molars. These findings highlight the potential of AI as a valuable tool for enhancing diagnostic precision in endodontics, especially in complex cases. However, further research is necessary to address the limitations of AI

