## **Study Design**

- Sample Size: 212 molars.
- Randomization: Not applicable (observational study).
- **Blinding**: Independent assessment by two experienced endodontists for CBCT and clinical examination.
- Control Group: Not applicable.

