Title: Diagnostic Accuracy of Artificial Intelligence, CBCT, and Clinical Examination in Detecting Number of Root Canals in Conventional and Retreated Maxillary and Mandibular Molars

NCT Number: “Pending”

Date: 29/10/2024

Statistical Analysis

Qualitative data were presented as frequencies and percentages. Friedman's test was used to compare between number of canals detected by the three methods. Kappastatistic was used to assess agreement between the threemethods. Kappa values ranging from 0.6 to 0.8 indicate good agreement while values ranging from 0.8 to 0.99 indicate very good agreement. Numerical data were explored for normality by checking the distribution of data and using tests of normality (Kolmogorov-Smirnov and Shapiro-Wilk tests). All data showed normal (parametric) distribution except for length of canal division from the apex and percentage of canal unity data which showed non-normal (non-parametric) distribution. Data were presented as mean, standard deviation (SD), median and range values. For parametric data, Student's t-test was used to compare between correctly and incorrectly diagnosedcases. For non-parametric data, MannWhitney U was used to compare between correctly and incorrectly diagnosed cases. Binary logistic regression model was constructed using diagnosis (Correct/Incorrect) as the dependent variable. Treatment, molar type, inter-orifice distance, percentage of canal unity and Vertucci classification were the independent variables. The significance level was set at $P \leq 0.05$. Statistical analysis was performed with IBM SPSS Statistics for Windows, Version 23.0. Armonk, NY: IBM Corp. ROC (Receiver Operating Characteristic) curve was constructed to determine the diagnostic accuracy measures of AI in relation to CBCT. Comparison between areas under the ROC curve (AUC) were performed using z-test. ROC curve analysis was performed with MedCalc® Statistical Software version 19.5.1 (MedCalc Software Ltd, Ostend, Belgium; <https://www.medcalc.org>; 2020)

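### Length of canal division is compared between correct and incorrect diagnoses only without adjustment, so a difference in tooth mix could be read as an effect of anatomy

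*SAP*

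**What the plan says.** The SAP (Statistical Analysis) sorts the numerical variables by normality. All are treated as normal "except for length of canal division from the apex and percentage of canal unity data which showed non-normal (non-parametric) distribution". Normal variables are compared between correct and incorrect diagnoses by Student's t-test. For the other two the rule is: "For non-parametric data, MannWhitney U was used to compare between correctly and incorrectly diagnosed cases". No strata or covariates are named, so pooling over all molars is the natural reading.

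One multivariable model follows: "Binary logistic regression model was constructed using diagnosis (Correct/Incorrect) as the dependent variable". Its covariates are listed in full: "Treatment, molar type, inter-orifice distance, percentage of canal unity and Vertucci classification were the independent variables". Length of canal division is not among them, and no reason is given. The threshold is "The significance level was set at $P \leq 0.05"; sidedness is not stated.

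The protocol's own Statistical Analysis Plan section is shorter and adds no adjusted analysis. Its introduction describes the sample as mixed; the aim is to compare methods "in detecting root canals in upper first, upper second, and lower first molars, in both conventional and retreatment cases". Study Design gives "Sample Size: 212 molars". The Results paragraph says: "There was no significant difference in AI accuracy between molar types, though the upper first molar had the highest accuracy (93.9"%), against 88.2% overall.

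**The concern.** Inter-orifice distance and percentage of canal unity are each examined twice, once unadjusted and once with molar type and treatment in the model. Length of canal division is examined once, unadjusted. By putting molar type and treatment in the model of diagnosis, the SAP itself treats them as relevant to whether a diagnosis is correct.

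Length is an absolute distance from the apex. It could differ between tooth types, though the documents give no data on this. If it does, and if errors are also unevenly spread over tooth types, the incorrect group contains a different mix of teeth from the correct group. The Mann-Whitney test would then pick up that mix. A reader could take the result to mean that where a canal divides affects whether it is detected, when within each molar type it makes no difference.

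**Working it through.** The documents state no power, effect size or error rate for this comparison, so there is no design figure to reproduce. The check has three steps.

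**1. Number of incorrect diagnoses.** Of 212 molars, 187/212 = 88.2%, which leaves 212 − 187 = 25 incorrect. No whole number out of 210 (the patient count in the protocol's Methods paragraph) rounds to 88.2%. This assumes that the SAP's correct/incorrect variable is the AI's diagnosis and that 88.2% is taken over all 212 molars.

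**2. Accuracy in the other molars.** The number of upper first molars is not given. Three sizes that reproduce 93.9% are used. The last column is a chi-square test over three types, splitting the other molars and their errors as evenly as whole numbers allow.

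| Upper first molars | Errors there | Errors elsewhere | Accuracy elsewhere | P, three types |
|---|---|---|---|---|
| 66 (62 correct) | 4 | 21 of 146 | 85.6% | 0.21 |
| 82 (77 correct) | 5 | 20 of 130 | 84.6% | 0.12 |
| 98 (92 correct) | 6 | 19 of 114 | 83.3% | 0.057 |

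All three are consistent with the reported lack of significance, the last one only barely. A non-significant result on about 25 errors therefore does not rule out a gap of this size, and does not establish one.

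**3. Behaviour of the pooled test.** Simulation with 4,000 runs per setting and a two-sided test at 0.05. Each molar is incorrect with the probability for its type from step 2. Length is normal, with a mean that differs by d within-type SD between upper first and other molars, and has no relation to diagnosis within type. The shifts d are assumptions.

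The comparator is the van Elteren test. In stratum s, with N molars, m of them incorrect, and R the rank sum of the incorrect ones, T = Σ [R − m(N+1)/2]/(N+1). Without ties, Var(T) = Σ m(N−m)/[12(N+1)], and z = T/√Var(T).

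| d (SD) | Pooled: 66 / 82 / 98 upper first molars | Stratified by type |
|---|---|---|
| 0.5 | 6.7 / 7.3 / 9.0% | 4.5–5.5% |
| 1.0 | 10.7 / 14.8 / 17.8% | 4.5–5.5% |
| 1.5 | 17.0 / 22.2 / 30.5% | 4.5–5.5% |

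A second simulation used skewed (gamma) lengths and type sizes of 71, 71 and 70:

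- Accuracy of 93.9% and 85.3% in each other type: pooled 7.1, 12.1 and 17.8% at the same shifts.
- Graded accuracy (93.9, 88.2 and 82.5%) with graded lengths: pooled 6.3, 13.2 and 21.3%.
- Equal accuracy of 88.2% in every type: pooled 4.7 to 5.3% at every shift, so no excess.
- Stratified test: about 5% throughout.

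A van Elteren test over six strata (three molar types by two treatments) also held about 4 to 6%.

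**The case against.** The strongest reply is that a reader might infer from the table that the Mann-Whitney test fails to hold its 0.05 level. The documents do not support that. The SAP states a marginal comparison of correct and incorrect cases. In the simulated settings with a shift, length does differ between those two groups, because their tooth mix differs, so rejecting is correct for the hypothesis as stated. It is a false positive only for a within-type hypothesis that the SAP does not state. This stands: the weakness lies in interpretation.

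Other parts of the reply also stand:

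- No passage calls length a predictor of misdiagnosis. The protocol's objective and hypothesis compare the accuracy of three methods, and its results say nothing about length.
- Length may overlap with percentage of canal unity, which is in the model. That could explain the omission, although the SAP does not say so.
- The sizes rest on inputs that the documents do not give. The largest figures need 98 upper first molars, the case at P = 0.057. If length can be measured in only 30% of molars (an assumption), the 82-molar rates fall to 5.5, 6.9 and 9.7%.
- Treatment was not simulated as a source of confounding, and no accuracy by treatment is reported.

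A reader might also infer that every pooled t and Mann-Whitney test needs replacing. That does not follow, because inter-orifice distance and canal unity already have an adjusted analysis in the logistic model.

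The reply does not remove the textual gap: length has no adjusted analysis, and the SAP does not mark its result as unadjusted.

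**Conclusion.** The point holds as a limit on interpretation. As the SAP stands, a significant result for length of canal division could not be separated from a difference in tooth mix.

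Whether this happens depends on two conditions that the documents do not settle: length must differ by molar type (or treatment), and so must diagnostic accuracy. If both do, with a true accuracy gap equal to the observed one, shifts of 0.5 to 1.5 SD and length recorded in all 212 molars, the pooled test rejects in about 6 to 31% of runs with no within-type effect. If accuracy is the same in every type, nothing is lost. The range is illustrative and does not estimate the bias in this study.

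The comparison is secondary and does not touch the main comparison of the three methods. The change is worth making because it is cheap.

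**What to change.** In the SAP's Statistical Analysis section, for length of canal division only:

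- Add a van Elteren (stratified Wilcoxon) test of correct against incorrect diagnosis, stratified by molar type and treatment, as the basis for any conclusion about length.
- Keep the pooled Mann-Whitney result if wanted, labelled unadjusted and descriptive.
- Leave the tests of canal unity and inter-orifice distance as they are.

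Adding length to the existing logistic model is less practical. With about 25 errors and roughly 12 parameters (assuming eight Vertucci classes), that model already has about 25/12 = 2.1 events per parameter.

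The cost is a sentence in the SAP and one rerun on variables already recorded. With 25 errors over six strata the average is about four per stratum (25/6 = 4.2), and a stratum with no incorrect molar contributes nothing, so a little information may be lost.

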#### **Statistical Analysis Plan**

- Descriptive analysis of frequencies and percentages.
- Friedman's test for comparison between methods.
- Kappa statistics for agreement between methods.
- ROC curve analysis to determine diagnostic accuracy measures (AUC comparison).

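### The SAP's ordinary logistic model of correct versus incorrect diagnosis is fragile if any Vertucci class is rare (about 25 errors if AI's diagnosis is modelled per molar); a Firth fit is a cheap remedy

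*SAP*

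**What the plan says.** The SAP (Statistical Analysis) states: "Binary logistic regression model was constructed using diagnosis (Correct/Incorrect) as the dependent variable". It then lists the predictors: "Treatment, molar type, inter-orifice distance, percentage of canal unity and Vertucci classification were the independent variables". It gives no number, coding, grouping or reference class for Vertucci, no penalised or exact method, and no rule for a class without errors. It does not say whose diagnosis is modelled, against what reference, or whether the unit is the tooth or the root.

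Numerical factors get a second analysis, by t-test or otherwise: "For non-parametric data, MannWhitney U was used to compare between correctly and incorrectly diagnosed cases". For categorical data the SAP offers only description: "Qualitative data were presented as frequencies and percentages". The logistic model is therefore the only test the SAP names of a link between Vertucci class and a wrong diagnosis.

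The model is absent from the protocol's own Statistical Analysis Plan list, which has entries such as "Kappa statistics for agreement between methods". Study Design gives 212 molars. The abstract's Results give the AI accuracy: "Overall, AI showed higher diagnostic accuracy (88.2" per cent). Its Introduction describes the teeth as "root canals in upper first, upper second, and lower first molars, in both conventional and retreatment cases", that is, three molar types and two treatment types.

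**The concern.** With few incorrect teeth and a categorical predictor of several levels, one level may contain no incorrect tooth. Ordinary maximum likelihood then has no finite solution for that level. Its coefficient runs off towards infinity, its standard error grows faster, and the Wald P-value goes to about 1. If the empty level is the reference, every Vertucci odds ratio is infinite.

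A Vertucci type that is never misdiagnosed, arguably the most informative pattern this model could show, could then be reported with an unbounded odds ratio and as non-significant, purely because of the fitting method. The overall Vertucci test would also miss its nominal level.

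**Working it through.** **Inputs.** From the documents: 212 molars (Study Design), AI accuracy 88.2% (abstract, Results), three molar types and two treatments (abstract, Introduction), five predictors and a 0.05 significance level (SAP). Assumed: AI is the modelled method, the molar is the unit, 88.2% uses the model's definition of correct, molar type and Vertucci are categorical, and Vertucci has the class counts and spreads shown below.

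**Step 1: number of incorrect teeth.** 212 × (1 − 0.882) = 25.0. Check: 187/212 = 88.21%, which reproduces 88.2%. On a base of 210 no whole number fits (25 errors give 88.10%, 24 give 88.57%). For bases from 90 to 212, no error count above 25 rounds to 88.2%. Smaller bases that fit give fewer errors, for example 12 in 102.

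**Step 2: slope parameters.** Treatment 1 + molar type 2 + two numerical predictors 2 + Vertucci (k − 1).

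| Vertucci classes k | Slopes | Incorrect teeth per slope |
|---|---|---|
| 2 | 6 | 25/6 = 4.2 |
| 3 | 7 | 25/7 = 3.6 |
| 5 | 9 | 25/9 = 2.8 |
| 8 | 12 | 25/12 = 2.1 |

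**Step 3: chance that one class has no incorrect tooth.** With errors unrelated to class, a class of n teeth is empty with probability C(212 − n, 25)/C(212, 25). This is 53% for n = 5, 28% for n = 10, 7% for n = 20, 1.7% for n = 30 and 0.3% for n = 42. The size of the class drives the risk.

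**Step 4: chance that at least one class is empty.** These are simulated. Ranges reflect separate simulations, which differ in whether class sizes are fixed or drawn at random.

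| Assumed spread (%) | Chance of an empty class |
|---|---|
| Two or three groups | 0 to about 3% |
| Five equal | 1.1 to 3.1% |
| Five: 40/25/20/10/5 | 33 to 34% |
| Five: 50/25/15/6/4 | 52% |
| Eight equal | 22 to 30% |
| Eight: 25/20/15/12/10/8/6/4 | 62 to 64% |
| Eight, strongly skewed | 94% |

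Five equal classes of about 42 teeth agree with the formula: 5 × 0.27% = 1.4% as an upper bound with sizes fixed. The chance that the rarest class is empty, which matters if it is the reference, is 28% for the 40/25/20/10/5 spread and 36 to 37% for the first uneven eight-class spread.

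**Step 5: effect on the tests.** When a Vertucci coefficient diverged, its Wald P had median 1.00 and minimum 0.997. With five or more separate classes and no true Vertucci effect, the overall test at nominal 5% rejected in 0.1 to 2.1% of runs (Wald) and 5.9 to 9.7% (likelihood ratio).

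**Step 6: Firth fit with the classes left as they are (600 runs per scenario).** Estimates were finite (largest absolute log odds ratio 4.4). The overall Vertucci test rejected in 2.8 to 5.5% of null runs. In the same runs ordinary Wald gave 0.2 to 3.2% and ordinary likelihood ratio 6.8 to 8.5%. With true effects spread over the classes, power was 28 to 54%, against 9 to 47% for Wald. The root mean squared error of the treatment log odds ratio fell in every coding, for example from 0.54 to 0.48.

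**Step 7: what the fix does not change.** For a treatment odds ratio of 2, power is about 35% with treatment as the only predictor and 31 to 36% in the full models. Low power there comes from having about 25 errors, not from the Vertucci specification.

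**Sensitivity.** If another method is modelled, no accuracy figure is given. Assuming 80% accuracy (212 × 0.20, about 42 errors), the empty-class chance falls to 0.1 to 13% for five classes and 4 to 78% for eight. With 12 errors in 102 teeth, five classes give 28 to 73%.

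**The case against.** The strongest objection is that the key facts are not in the documents. A reader might infer that the SAP enters five or more Vertucci classes against at most 25 AI errors. The documents do not support that. They give neither the number nor the spread of classes, and silence about grouping does not show that none was used. The count of 25 needs AI as the modelled method and the molar as the unit. The nearby ROC analysis "was constructed to determine the diagnostic accuracy measures of AI in relation to CBCT" makes AI plausible, but the regression sentence names no method. Some predictors could be recorded per root, which would change the count. All of this stands, so the point must be conditional. It is also true that rarity of a class matters, not the number five: five equal classes carry a risk of only 1 to 3%.

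A reader might also infer that Vertucci has to be collapsed into two or three groups. That does not follow. Grouping does bring ordinary tests closer to their level (3.6 to 6.1% in simulation). But it loses detail, loses power if the groups miss the true pattern, and would now be chosen after results are known, since the abstract already reports them. Firth does not need it.

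Finally, little depends on this model. It is secondary, and the abstract draws no conclusion about Vertucci. That limits the severity. It does not remove the point, because a better fitting method is available at almost no cost even with few classes.

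**Conclusion.** The concern holds in conditional form, as a minor point. The SAP specifies ordinary logistic regression with no sparse-data method. Under the assumptions listed in the working, about 25 incorrect teeth support 6 or more slopes. If a Vertucci class is rare, an infinite odds ratio with a Wald P near 1 is a real possibility, and neither ordinary overall test of Vertucci holds its level. With two or three groups, or with Vertucci entered as a single numerical term, most of the problem disappears.

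The wide span of the empty-class risk reflects assumed spreads and is not an estimate for this trial. The point does not show that the treatment or molar-type results are invalid, and it does not touch the comparison of AI, CBCT and clinical examination. Confidence is medium, because the class distribution, the unit and the modelled method are not stated.

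**What to change.** In the SAP, fit this model by Firth penalised likelihood, with profile-likelihood confidence intervals and penalised likelihood-ratio tests. Keep all five predictors and the Vertucci classes as recorded, and report the number of incorrect teeth in each class. Grouping by anatomy is optional. If it is used, label it post hoc.

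For clarity, also state the unit of analysis, whose diagnosis is modelled and against which reference it is judged, and the Vertucci reference class.

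The cost is a few lines of text and one re-run in software that supports Firth regression. There are two downsides: the overall Vertucci test is slightly conservative with many classes (about 3% at nominal 5%), and intervals for the other factors stay wide.

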# **Study Objectives and Hypotheses**

• **Objective**: To evaluate and compare the accuracy of AI, CBCT, and clinical examination in detecting the number of root canals in maxillary and mandibular molars.

• **Hypothesis**: AI will demonstrate superior diagnostic accuracy compared to CBCT and clinical examination.

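### Accuracy of the canal count is assigned to an ROC of AI against CBCT with no stated target, score, cut-off or AUC pair; no reading of it can test the whole superiority hypothesis, and no proportion correct with a confidence interval is planned

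*SAP*

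**What the plan says.** The protocol's objective is to "compare the accuracy of AI, CBCT, and clinical examination in detecting the number of root canals", and its hypothesis is that "AI will demonstrate superior diagnostic accuracy compared to CBCT and clinical examination" (Study Objectives and Hypotheses). Study Procedures makes the recorded quantity a number of canals per tooth, compared across the three methods.

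Both documents assign accuracy to an ROC analysis. The protocol's Statistical Analysis Plan lists ROC analysis with an AUC comparison and adds no detail. The SAP says "ROC (Receiver Operating Characteristic) curve was constructed to determine the diagnostic accuracy measures of AI in relation to CBCT", followed by "Comparison between areas under the ROC curve (AUC) were performed using z-test".

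Other parts of the plan bear on accuracy:

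- The SAP states "Qualitative data were presented as frequencies and percentages".
- It plans kappa for agreement and Friedman's test on the counts.
- It compares correctly with incorrectly diagnosed cases, and states "Binary logistic regression model was constructed using diagnosis (Correct/Incorrect) as the dependent variable". Of that model it says "Treatment, molar type, inter-orifice distance, percentage of canal unity and Vertucci classification were the independent variables".
- The summary that opens the protocol names sensitivity and specificity, and reports AI accuracy of 88.2% overall and 93.9% for the upper first molar.

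Neither document mentions a confidence interval.

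**The concern.** An ROC curve needs a yes/no condition and a score, and sensitivity and specificity also need a cut-off. A canal count supplies none of these until someone chooses, for example, four or more canals as the positive state. The plan makes no such choice and does not name the AUCs to be compared. The same gap affects the regression, the t-tests and the Mann-Whitney tests, because all of them use correct versus incorrect without saying whose diagnosis is judged or against what.

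Two things are at stake. First, a superiority claim needs a reference that is not one of the methods being beaten, and the documents point to two different references. The SAP's ROC sentence suggests CBCT. The protocol summary describes a five-canal tooth found at clinical examination as missed by the other two methods, which treats the clinical count as the truth. Against the clinical count, AI is wrong on that tooth; against CBCT, AI is right if the two gave the same number.

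Second, an AUC can change with the mix of three- and four-canal teeth, the direction of the errors or the chosen target while the share of correctly counted teeth stays the same. An AUC, or a z-test between AUCs, may then be read as a statement about counting accuracy that it is not.

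**Working it through.** **1. The reported figure.** The protocol summary gives 88.2% with no numerator, denominator or reference, so it cannot be reproduced from stated inputs. Study Design gives 212 molars and the summary gives 210 patients.

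- Over 212: 186/212 = 87.7%, 187/212 = 88.2%, 188/212 = 88.7%. Only 187 fits.
- Over 210: 185/210 = 88.1%, 186/210 = 88.6%. Nothing fits.

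If the denominator is 212, the figure is consistent with a simple proportion of 187/212. This is an inference. The exact (Clopper-Pearson) 95% limits are the 2.5% point of Beta(187, 26) and the 97.5% point of Beta(188, 25), which give 83.1% to 92.2%, treating teeth as independent.

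**2. What each reading of the ROC sentence can test.**

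| Reading | Reference | AI vs CBCT | AI vs clinical examination |
|---|---|---|---|
| AI judged against CBCT | CBCT | Not testable: CBCT is correct by construction | Not addressed by this ROC |
| AI and CBCT curves both judged against the clinical count | Clinical examination | Could be tested | Not testable: the clinical count is correct by construction |

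The hypothesis claims both comparisons, and neither row delivers both. Friedman's test compares counts and kappa measures agreement, so neither tests correctness.

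**3. AUC against proportion correct.** These are constructed tables, not trial data: 212 teeth, reference counts of 3 or 4, AI counts of 3 or 4, 187 correct and 25 wrong, target four or more. With a two-valued score, AUC = (sensitivity + specificity)/2. Balanced means 12 fours read as three and 13 threes read as four.

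| Four-canal share (fours/threes) | All errors 4-to-3 | All errors 3-to-4 | Balanced |
|---|---|---|---|
| 20% (42/170) | (17/42 + 1)/2 = 0.702 | (1 + 145/170)/2 = 0.926 | (30/42 + 157/170)/2 = 0.819 |
| 50% (106/106) | (81/106 + 1)/2 = 0.882 | 0.882 | (94/106 + 93/106)/2 = 0.882 |
| 80% (170/42) | (145/170 + 1)/2 = 0.926 | (1 + 17/42)/2 = 0.702 | (158/170 + 29/42)/2 = 0.810 |

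The proportion correct is 88.2% in every cell. AUC equals it at a 50% share and departs from it elsewhere.

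**4. Target and score.** Take another assumed table, with reference counts 2, 3 and 4 in rows and AI counts 2, 3 and 4 in columns: (8, 4, 0), (1, 95, 12), (0, 8, 84). Again 187 of 212 agree.

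- Target three or more, single cut: (199/200 + 8/12)/2 = 0.83.
- Target four or more, single cut: (84/92 + 108/120)/2 = 0.91.
- Target three or more, with the whole AI count as score: 0.91.

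**5. A z-test between groups.** As an extreme illustration, take two independent groups of 70 teeth, each with 62/70 correct and all 8 errors 4-to-3. The DeLong variance reduces here to ¼[Se(1−Se)/(n₄−1) + Sp(1−Sp)/(n₃−1)], where n₄ and n₃ are the numbers of four- and three-canal teeth.

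| Four-canal shares | AUCs | z | p |
|---|---|---|---|
| 20% / 80% | (6/14 + 1)/2 = 0.714; (48/56 + 1)/2 = 0.929 | 2.95 | 0.003 |
| 30% / 70% | 0.810; 0.918 | 1.80 | 0.07 |
| 40% / 60% | 0.857; 0.905 | 0.90 | 0.37 |

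For the first row, the variances are 0.00471 and 0.00056, so z = 0.214/√0.00527 = 2.95. With balanced errors (4 and 4), the two AUCs are equal only when the shares mirror each other, as 20% and 80% do. Shares of 20% and 50% give 0.821 and 0.886 (p = 0.40).

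**The case against.** The plan is not empty on accuracy. Correct/Incorrect is a qualitative variable, so the planned percentages could cover a proportion correct. Sensitivity, specificity and kappa are named, the regression already contains molar type, and the reported 88.2% may well be a simple proportion. This stands: what is missing is the definition, the reference, the method judged and the interval, not every trace of a percentage.

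The ROC sentence need not make CBCT the reference. It can be read as AI's curve set beside CBCT's, both against clinical examination. That gives the z-test a natural pair and fits the description of the five-canal tooth. This also stands, so the statement that AI cannot beat CBCT is conditional on the first reading. It does not rescue the hypothesis, because the second reading removes the comparison with clinical examination.

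The p = 0.003 example is a corner case. It needs every error in one direction, widely different four-canal shares, and 8 of 14 four-canal teeth misread in one group. It shows what is possible, not what is likely.

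Finally, a well-defined target such as four or more canals, with sensitivity, specificity and AUC, is a legitimate analysis. That is so, but it answers whether a tooth passes a threshold. The stated objective is the number of canals.

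**Conclusion.** The accuracy analysis is wrong as written, not merely brief. Its target, score, cut-off and AUC pair are unstated, correctness has no reference, and under either reading of the ROC sentence the hypothesis of superiority over both other methods is not testable by it. That conclusion needs no assumption about the data.

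The sizes do rest on assumptions. The AUC ranges of 0.70 to 0.93 and 0.81 to 0.88 come from constructed tables with two reference counts and a target of four or more. The interval of 83.1% to 92.2% assumes that 88.2% means 187 of 212 independent teeth.

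A reader might infer more than the documents support:

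- That the 88.2% is a distorted AUC. No AUC value is reported in either document, and the figure fits a proportion.
- That the z-test produced a false difference between molar types. Neither document says the z-test compares molar types, and the protocol summary reports no significant difference between them.
- That CBCT is definitely the reference. The wording is ambiguous.

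**What to change.** 1. Name one reference. Define correct as the AI count equal to the count from that reference.
2. Make the proportion correct, with an exact 95% confidence interval, the accuracy measure, overall and by molar type. State that the molar-type term in the planned regression is the test by molar type.
3. Keep sensitivity, specificity or AUC only as secondary measures, with the yes/no target, score, cut-off and AUC pair stated. Since results already appear in the protocol summary, label as post hoc any of these chosen after they were seen.
4. Compare two methods by McNemar's test only where the reference is neither of them and is independent of both. This independence has to be shown: AI reads the same CBCT scans as the endodontists, and the documents do not say that the CBCT readers and the clinical examiners are different people.
5. Do not claim that AI is superior to whichever method serves as reference. Report exact agreement with it instead.

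The cost is SAP wording, tables from counts already held and possible re-coding of some teeth against the named reference. The superiority claim also becomes narrower. The documents identify no reference clearly independent of all three methods, so the full hypothesis may not be testable with the data recorded, and the report should say so.
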